2.6 RECRUITMENT OF PARTICIPANTS (SAMPLING)

School eligibility

Intervention status will be randomly assigned to 132 schools across the Schools Division of Zamboanga del Norte (ZDN) Province, resulting in 66 schools per arm.

To be eligible for the intervention and study, schools will need to meet a set of minimum inclusion criteria. This is intended to ensure that schools participating have the required infrastructure in place for the intervention to be effective. The minimum inclusion criteria will include:

- (i) Water for handwashing was available at the school for at least certain days of the week
- (ii) The overall pupil to toilet ratio equaled 100 or lower
- (iii) School has at least one individual or group handwashing station
- (iv) School is situated in a district deemed safe by DepEd²⁸
- (v) School does not have any planned WASH programming in the upcoming 2019-20 school year beyond standard WinS activities

We used data from DepEd's WinS Online Monitoring System (OMS) tsto assess the eligibility of public elementary schools. DepEd division offices collect this data via self-assessment by schools. Based on the alignment between initial observations from our scoping and piloting trip for the study and the OMS data, we believe this data is reliable. We can further confirm these assumptions with data from Research Question 2 (RQ2).

Based on the above, 210 out of 634 (33%) schools were eligible for random selection.

Randomization procedure

²⁸Within Zamboanga del Norte, DepEd has identified all school districts within Zone 1-3 and several in Zone 4, as sites for the study. DepEd excluded the remaining school districts within the division due to safety and accessibility concerns.

Schools were assigned to treatment or control group based on a two-step stratified randomization procedure. Stratification ensures the schools are balanced across relevant characteristics that may affect our outcome of interest. In our case, our strata were determined by the "WinS implementation quality index score" (WinS IQ). Each school was assigned a WinS IQ score using data from the OMS. These criteria capture whether schools have infrastructure conducive to our outcomes of interest. Scores ranged from 0 to 9 based on how many of the criteria they met, and was based on a series of nine sanitation, hygiene, and overall WASH indicators.²⁹

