We also determined variables in the OMS data that may indicate that the school has basic features which are conducive to the nudge intervention, or "nudge enabling" features. Specifically:

- No Information, Education, and Communications (IEC) campaign materials on hygiene in toilets or handwashing areas
- Toilets have lights

We categorized schools as having "nudge enabling" features based on whether a combination of these basic criteria were satisfied³⁰. We determined 114 schools had such features.

First, we randomly sampled 100 of these 114 "nudge enabled" schools. We randomly assigned 50 schools to treatment group and 50 schools to control group, stratifying by three categories of WINS quality index scores (Low 2-5, Medium 6-7, and High 8-9). Within our sample of 132 schools, we oversampled "nudge enabled" schools in an attempt to hold constant bathroom environments across schools in our evaluation sample. This was done out of the concern that substantial differences in bathroom environments at baseline (for instance, some more cluttered than others) may dilute the effect of nudges.

To achieve our final sample of 132 schools, 32 supplementary schools were randomly drawn from the 96 non-nudge enabler schools remaining in the eligible population. Again, half were randomly assigned to treatment group and half were randomly assigned to control group within each WiNS index strata to ensure balance on this key variable. Note, this was done in order to introduce variation in baseline handwashing environment, since we hypothesize this is an important mediator for the impact of nudges. This procedure aims to ensure that the nudges are installed in more environments likely to be conductive to them, as such environments would also be targeted in any scale-up decision.

However, we will not be comparing treatment effects in nudge-enabled and non-nudge-enabled schools. We constructed the "nudge-enabled" indicator only to identify schools more likely to have non-cluttered facilities, in order that we can select for a higher probability of non-cluttered classrooms during sampling, as such classrooms would likely be more conducive to the nudges. This indicator was created using available school-level administrative data. However, in our evaluation, we are ultimately interested in the effect of "clutteredness" at the handwashing facility-level (rather than the school-level) on the impact of the nudges. Therefore, rather than using our "nudge-enabled" constructed

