Unit	Co-variate	Metric	Hypothesized relationship to outcome
	District Number of pupils enrolled (pre- intervention)	 X.1 – categorical variable where each value category represents the school district where the school is located X.2 – continuous variable to represent the number of pupils enrolled at the elementary school prior to intervention³⁷ X.3 – index variable between 0 and 11 	 School district is associated with geographic location, which may be associated with varying levels of rurality, access to water, socio-economic status of teachers and pupils, or support received from DepEd division office. Given that school budget is partially determined by number of pupils enrolled, and that larger schools tend to be located in urban or semi-urban areas, school resources and the school pupil and teacher population may vary depending on school size. This will be estimated using information reported by principals during end-line school visits or using the data reported in DepEd's Online Monitoring System (OMS), depending on how reliably information reported by principals can be collected.
School	WinS implementatio n quality index score (pre- intervention)	composed of 11 binary indicators related to WASH conditions at the school, as reported in OMS data by principals prior to the intervention ³⁸	Higher score indicates a higher level of reported quality of WinS implementation, and may thus be associated with a higher level of handwashing infrastructure and supplies, as well as more consistent implementation of WinS program activities involving pupils, such as group handwashing and tooth- brushing.
	Nudge- enabled	X.4–binary variable for whether school is "nudge-enabled" or not "nudge-enabled"	Nudge-enabled schools are those with combinations of features that indicate they may be more conducive to nudge intervention than schools without those features. Please see Section 2.5 Recruitment of Participants (Sampling) for details of these nudge-enabling features. Because of the presence of these features, the nudge intervention may have greater impact on nudge-enabled schools than schools that are not.

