Class	Number of pupils in the classroom	X.5 – continuous variable where value represents the number of pupils present in the classroom during the observation period	Classroom size may be associated with school resources and teacher quality or attention, which may influence pupil opportunity and incentives to wash hands with soap. Further, if handwashing with soap after toilet use is considered to be a norm (or habit) that the nudges remind pupils of, and if the class is considered as the primary 'social unit' for this norm, the number of pupils in this social unit may influence the likelihood of the norm arising and persisting.

Table 4: Control Variables for Research Question 1

³⁷ This variable may be converted to an ordinal variable to mitigate random error due to imprecision in the number of pupils reported.

³⁸ See Table 7 in the *Sampling* section of the evaluation design document for a description of 11 indicators an additional information on the online monitoring system (OMS) Evaluation Design Document

Pre-analysis plan [DRAFT] | January 20, 2020

	Nudge- conducive	X.6 - Binary variable indicating whether the handwashing area location near/in the classroom is "nudge conducive"	Nudge-conducive handwashing areas are those with combinations of features that indicate they may be more conducive to nudge intervention than handwashing areas without those features. Please see Section 3.2 Data Collection Activities for details of these nudge-conducive features. The nudge intervention may have greater impact for nudge-conducive handwashing areas than non-nudge conducive areas.
Unit	Co-variate	Metric	Hypothesized relationship to outcome
Pupil	Gender	X.7 – binary variable for whether pupil observed is female	Traditional gender roles tend to involve more tasks that may require handwashing for girls than boys, such as cooking or cleaning, and may thus facilitate building handwashing habits among girls.
	Grade	X.8 – categorical variable where each	The behavioral nudges targeted at changing pupil behavior may be more engaging and/or effectively

1.c. Analytic model

Specification for LPM: The effect of the treatment on the outcome variables listed in **Error! R** eference source not found. for which the analytic model indicated is the Linear Probability Model will be measured by conducting the following regression:

$$Y_{ij} = \beta_0 + \beta_1 T_j + \overrightarrow{\beta_2} \vec{X}_{2ij} + \varepsilon_{ij}$$

Where:

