 $^{^{\}rm 39}$ Observations in which the student grade was unknown will be excluded.

Pre-analysis plan [DRAFT] | January 20, 2020

1.d.iv. Treatment impact by WinS implementation quality index score: In order to compare the average effect of the nudges intervention on the outcome of independent handwashing after toilet use across different levels of WinS implementation quality, sub-group analysis will be conducted using the following regression:

$$Y_{ij} = \beta_0 + \beta_1 T_j + \beta_2 W_j + \beta_3 (T_j \times W_j) + \overrightarrow{\beta_4} \overrightarrow{X}_{4ij} + \varepsilon_{ij}$$

Where:

- *W_j* is an ordinal variable between 0 and 11 denoting the WinS implementation quality index score for school *j*
- \vec{X}_{4ij} represents a vector of pupil, school, and class level co-variates as specified in Table 2, excluding WinS implementation quality index score
- All other regression terms are defined as they were in the previous regression specification and β₃ is the coefficient of interest.

1.d.v. Treatment impact by nudge conduciveness: In order to compare the average effect of the nudges intervention on the outcome of independent handwashing after toilet use depending on the context's conduciveness to nudges, sub-group analysis will be conducted using the following regression:

Where:

$$Y_{ij} = \beta_0 + \beta_1 T_j + \beta_2 W_j + \beta_3 (T_j \times N_i) + \beta_4 X_{4ij} + \varepsilon_{ij}$$

- N_i will be a binary variable (to be constructed after seeing the distribution) =1 if the pupil
 was exposed to a nudge-conducive handwashing environment at the time of toiet use and
 =0 if not
- \vec{X}_{4ij} represents a vector of pupil, school, and class level co-variates as specified in Table 2, excluding WinS implementation quality index score
- All other regression terms are defined as they were in the previous regression specification and β₃ is the coefficient of interest.

1.e. Presentation of results: a regression table will be included for each specification to describe the correlation between key indicators of interest and co-variates. Data visualizations describing the level of the outcomes variables in the treatment and control group may also be included.

RESEARCH QUESTION 2

2.a Research question 2: What is the causal impact of the behavioral nudge intervention on pupil access to handwashing facilities with soap and water?

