- L_k is a dummy variable denoting whether toilet facility k is located inside a classroom
- \vec{X}_{4j} represents a vector of school level co-variates as specified in sub-section 2.b, excluding location of toilet facility
- ϵ_{kj} denotes the facility error term k, clustered at the school-level to reflect the fact that the treatment assignment was at the school level
- β_n denotes the coefficients determined by the regression model (β₃ is coefficient of interest)

2.d.ii. *Treatment impact by WinS implementation quality index score*: In order to compare the average effect of the nudges intervention on the outcome of presence of a functioning handwashing facility with soap near school toilets across different levels of WinS implementation quality, sub-group analysis will be conducted using the following regression:

$$Y_{kj} = \beta_0 + \beta_1 T_j + \beta_2 W_j + \beta_3 (T_j \times W_j) + \overrightarrow{\beta_4} \vec{X}_{4kj} + \varepsilon_j$$

Where:

- W_j is an ordinal variable between 0 and 11 denoting the WinS implementation quality index score
- \vec{X}_{4kj} represents a vector of school and facility level co-variates as specified in sub-section 2.b, excluding WinS implementation quality index score
- All other regression terms are defined as they were in the previous regression specification and β₃ is the coefficient of interest

2.e. Presentation of results: a regression table will be included for each specification to describe the correlation between key indicators of interest and co-variates. Data visualizations describing the level of the outcomes variables in the treatment and control group may also be included.

MULTIPLE HYPOTHESIS TESTING CORRECTION

Subgroup analyses and analyzing multiple indicators of the same category of outcomes increases the number of hypotheses being tested. As such, standard statistical significance levels would likely result in finding significant coefficients by chance alone (i.e., false positives). To correct for this increased likelihood of false positives, the analysis will be adjusted for multiple inference using the

Holm-Bonferroni procedure⁴¹. The correction will impose a more conservative threshold for statistical significance. Normal, uncorrected p-values will also be reported.

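### Schools were randomised within WinS band and nudge-enabled strata, but no RQ1 or RQ2 model carries stratum indicators; separately, one name covers a nine-item and an eleven-item WinS score

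*SAP*

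**What the plan says.** **Randomisation (SAP 2.6).** Assignment took two steps. From the nudge-enabled schools, 100 were drawn and split 50/50, "stratifying by three categories of WINS quality index scores (Low 2-5, Medium 6-7, and High 8-9". A further 32 schools were drawn from those not nudge-enabled and split in half "within each WiNS index strata to ensure balance on this key variable". The bands used in the second step are not spelled out. If they are the same three, the design has 2 x 3 = 6 strata.

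**Models (SAP 6).**
- RQ1 is to be reported both with and without covariates. The covariates come from Table 4, which lists the WinS score as X.3 and nudge-enabled status as X.4.
- RQ2 (2.b) takes district and the WinS score. For facility-level outcomes it adds enrolment and toilet location. Nudge-enabled status is not listed.
- No equation in 1.c, 1.d, 2.c or 2.d has a term for WinS band or stratum.

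**The WinS score.** In 2.6, "Scores ranged from 0 to 9 based on how many of the criteria they met", and the score "was based on a series of nine sanitation, hygiene, and overall WASH indicators". In Table 4, X.3 runs from 0 to 11 and is "composed of 11 binary indicators related to WASH conditions at the school"; its footnote 38 points to another document's "section of the evaluation design document for a description of 11 indicators". In 1.d.iv the moderator W_j "is an ordinal variable between 0 and 11 denoting the WinS implementation quality index score for school", and 2.d.ii gives the same range.

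**The concern.** Stratified assignment forces the arms to agree on the stratifiers, so the treatment estimate varies less from one randomisation to another. A model without the strata does not see this. It leaves between-stratum variation in the residual, so the standard error is too large and the test too cautious. Section 2.6 justifies the stratification by saying these characteristics may affect the outcome. If so, the plan pays for precision in the design and does not collect it in the analysis. The plan does not say whether the controlled or the uncontrolled RQ1 estimate is primary, so the uncontrolled one cannot be set aside.

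The WinS mismatch is a separate matter of definition. The score is a covariate in RQ1 and RQ2 and the moderator in an interaction test in each. A reader cannot tell from this plan whether X.3 is the variable that defined the strata or a different index with the same name.

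**Working it through.** **1. The plan's own figure.** Inputs from 2.5: 10% against 17%, ICC 0.1, 26 pupils per school, alpha 0.05 (taken as two-sided), power 0.80.
- Design effect = 1 + 25 x 0.1 = 3.5.
- Unpooled two-proportion formula: (1.960 + 0.842)^2 x (0.10 x 0.90 + 0.17 x 0.83) / 0.07^2 = 370.2 pupils per arm.
- Schools per arm = 370.2 x 3.5 / 26 = 49.8, so 100 in total.

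The stated 100 schools reproduces. The pooled formula gives 102. Nothing below changes the sample size.

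**2. Uncontrolled RQ1, pooled grades.** Let R2 be the share of between-school variance that the strata explain. The documents give no value, so a range is used.
- Mean rate 0.135; v = 0.135 x 0.865 = 0.1168.
- Standard error the uncontrolled model works with: sqrt(2v(0.1 + 0.9/26)/k), k schools per arm. The bracket is 0.1346, so SE = 0.0218 (k = 66) or 0.0251 (k = 50).
- True standard error under stratified 1:1 assignment: sqrt(2v(0.1(1 - R2) + 0.9/26)/k).
- True alpha, uncontrolled = 2(1 - Phi(1.96 x SE_model/SE_true)).
- Power, uncontrolled = Phi((0.07 - 1.96 x SE_model)/SE_true).
- Power with strata = Phi(0.07/SE_true - 1.96).

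| R2 | True alpha, no strata | 132 schools: without / with strata | Points lost | 100 schools: without / with strata | Points lost |
|---|---|---|---|---|---|
| 0 | 0.050 | 0.894 / 0.894 | 0 | 0.797 / 0.797 | 0 |
| 0.02 | 0.048 | 0.896 / 0.898 | 0.3 | 0.799 / 0.803 | 0.4 |
| 0.05 | 0.046 | 0.898 / 0.905 | 0.7 | 0.802 / 0.812 | 1.0 |
| 0.10 | 0.042 | 0.903 / 0.915 | 1.3 | 0.806 / 0.827 | 2.0 |
| 0.20 | 0.034 | 0.912 / 0.935 | 2.3 | 0.816 / 0.857 | 4.0 |
| 0.40 | 0.019 | 0.932 / 0.969 | 3.7 | 0.839 / 0.915 | 7.5 |

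Losses are taken before rounding. Alpha never exceeds 0.05.

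**3. Uncontrolled RQ1, one grade group (13 pupils per school, from 2.5).** The bracket becomes 0.1 + 0.9/13 = 0.1692. Power at R2 = 0 is 0.816 (132 schools) or 0.702 (100). The loss is 0.3 to 1.5 points at R2 of 2 to 10% and 3.0 to 5.7 at 20 to 40% with 132 schools. With 100 schools it is 0.4 to 2.0 and 4.2 to 8.5.

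**4. What the listed covariates recover.** This is a simulation of 4,000 trials with 132 schools and the RQ1 planning inputs. R2 is 0.3, half from WinS and half from nudge-enabled status, and the score entered is the one that defines the bands. Cells are type I error / power at 7 points.

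| Model | WinS effect linear in score | WinS effect a non-monotone step by band |
|---|---|---|
| No covariates | 0.027 / 0.906 | 0.027 / 0.913 |
| Score only (RQ2's pattern) | 0.037 / 0.927 | 0.028 / 0.912 |
| Score + nudge-enabled (controlled RQ1) | 0.048 / 0.944 | 0.036 / 0.931 |
| Stratum indicators | 0.050 / 0.939 | 0.048 / 0.947 |

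The score-only row uses the RQ1 outcome and only illustrates the pattern. The SAP has no planning inputs for RQ2, so no size is claimed there.

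**5. Cost of the indicators if strata explain nothing.** Simulated power (8,000 trials, assumed stratum sizes) is 0.888 without and 0.887 with six strata at 132 schools, and 0.789 against 0.788 at 100: about 0.1 point.

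**6. The WinS score side by side.** In 2.6 there are nine indicators, range 0-9, top band 8-9. Table 4 has eleven indicators and range 0-11; 1.d.iv and 2.d.ii give 0-11. Both sets are internally consistent, so neither is a stray digit. No sentence links them.

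**The case against.** The strongest reply is that both stratifiers are already in the RQ1 model the plan writes out. Table 4 supplies X.3 and X.4, and the 1.c equation carries that covariate vector. This stands. If the WinS effect is roughly linear in the score, controlled RQ1 loses nothing against stratum indicators. With a deliberately awkward step effect it loses about 1.6 points in the table above (0.947 - 0.931). A reader might infer that no model takes any account of the stratification. That is too strong: the omission is complete only in uncontrolled RQ1 and partial in RQ2.

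It is also fair that the gain may be small. Footnote 29 says earlier assessments found that facilities were not the main barrier to handwashing, which points to a low explained share. Power at 132 schools is already 0.894 against a target of 0.80. The largest loss, 8.5 points, needs 40% explained, one grade group and 32 schools lost together.

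Section 2.6 says effects will not be compared by nudge-enabled status and that the indicator was built for sampling. Stratum main effects make no such comparison, and Table 4 already uses the indicator as a control.

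On the score, the mismatch might be read as leaving the analysis variable open until after endline. The text does not support that: Table 4, 1.d.iv and 2.d.ii all use 0-11. Footnote 38 cites a description of eleven indicators in a document not at hand, so two indices may exist on purpose. What remains is that this plan does not say so.

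**Conclusion.** The point holds in limited form. The randomisation strata do not appear as indicators in any RQ1 or RQ2 model. The consequence is a conservative test and some lost precision, mainly in uncontrolled RQ1: for pooled grades about 0.3 to 1.3 power points at 132 schools if strata explain 2 to 10% of between-school variance, and 2.3 to 3.7 at 20 to 40%. At the planned minimum of 100 schools it is 0.4 to 2.0 and 4.0 to 7.5. The explained share and two-sided testing are assumptions; the other inputs are the plan's.

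A reader might infer that ignoring the strata biases the estimate or inflates false positives. Under 1:1 allocation within strata it does neither; alpha falls below 0.05.

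The two descriptions of the WinS score do conflict, and this needs no assumption. It is a gap in explanation, since the models themselves use the 0-11 version throughout. No numerical harm is claimed for it.

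**What to change.** 1. Add indicators for the strata actually used at randomisation (WinS band x nudge-enabled) to every RQ1 and RQ2 model, including RQ1 without other covariates. State the bands used in the second step.
2. Drop X.4 wherever these indicators enter. It is the sum of the nudge-enabled stratum indicators and so exactly collinear with them. X.3 can stay, because it can vary within a band.
3. Reconcile the nine-item and eleven-item descriptions of the WinS score. Alternatively, state that two indices exist, that the 0-9 one formed the strata, and that the 0-11 one is X.3 and W_j, with distinct names.
4. Editorial only: 1.c and 2.c describe T_j as receipt of the intervention, while footnotes 36 and 40 and the intent-to-treat statement in Section 4 make it assignment. Align the wording.

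The cost is SAP text. The strata were fixed at randomisation, so no new data are needed. With six strata the indicators use at most five degrees of freedom out of 132 schools, or a net four (5 - 1) in controlled RQ1 once X.4 is dropped.

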2.7 STAKEHOLDER ENGAGEMENT

This study is led by IDinsight in close partnership with the WASH section of UNICEF Philippines. The project's stakeholders and roles are as follows:

- **UNICEF** WASH team will advise on the intervention, convene and build consensus among stakeholders, and fund intervention design, implementation, and elements of the study
- Zamboanga del Norte DepEd will support the intervention design and implementation, provide routine monitoring and support to schools during implementation process, and advise IDinsight on safety and security matters
- **IDinsight** will design the intervention, manage the intervention implementation, and evaluate the program
- WASHPaLS will fund the majority of the evaluation and provide technical oversight

IDinsight will solicit and incorporate both DepEd and UNICEF's contextual knowledge of Zamboanga del Norte schools and the region to strengthen the nudge design and evaluation design. The intervention will be tested as part of DepEd's national WinS policy, and will serve as part of UNICEF's strategic focus on improved hygiene and handwashing in schools. IDinsight will present evaluation

results and discussion implications with UNICEF, DepEd, and WASHPaLS at the conclusion of the study. IDinsight will also work with all parties to disseminate the study process and results to add to the global WASH knowledge and practice, especially around iHWWS.

Pre-analysis plan [DRAFT] | January 20, 2020

